## **GUIDELINES FOR REMOTE DATA COLLECTION**

1. Highest priorities: the subject safety and preserving integrity of data are critical
2. Study visits and procedures must be followed per protocol whenever possible. Any specific changes in study conduct that deviate from the protocol should be communicated to the IRB and Sponsor (via reporting to your site assigned CRA). All protocol deviations which occurred as a result of COVID-19 disruptions (e.g., visits out of window, missed assessments, etc.) should be differentiated from other PDs. It is prudent to receive IRB guidance or approval if a deviation is known to occur in advance (i.e., extending IP application or changing assessment windows, etc.).
3. If, despite all efforts, a planned clinic visit is absolutely not possible due to a COVID-19 related issue (e.g., site has closed, subject prohibited from coming to clinic, etc.), sponsor's strong preference is a delayed clinic visit. If the subject can come to clinic within a reasonable amount of time considering the protocol allowed visit window. If a delayed clinic visit cannot be completed within 14 days of the protocol specified visit window, please contact the Medical Monitor for additional guidance.
4. It is critical to ensure subjects have enough IP in the event timely clinic visit(s) is/are not possible. It is also critical to ensure subjects are instructed to continue to apply IP per protocol for the duration of their participation in the study. Subjects should also be reminded to complete their daily diaries and IP compliance should be assessed via phone if clinic visits are not possible or are delayed.
5. It is critical for preserving data integrity to make every effort possible to have a subject return to clinic for the Week 4 visit. For visits conducted in the clinic, it is critical to ensure Rater consistency for all efficacy assessments (e.g., IGA, etc.). If absolutely necessary, it is preferred to have several missed visits and a delayed Week 4 visit versus having an Early Termination and no Week 4 visit. If it is not possible for a subject to return on-site within window for the Week 4 visit, sites should:
  - a. Ensure the subject has signed the most current IRB approved ICF with the ICF Addendum.
  - b. Contact subjects to discuss continued administration of IP and continue to complete their dosing diaries per regular IP administration instructions.
  - c. Subjects are approved to continue applying IP post Week 4 as long as the following have been discussed with the subject:

- Site should confirm the subject has adequate IP to continue dosing and if not ask the subject to return to the site to pick up additional IP or refer to the current IP Handling Plan for instructions on shipment of IP from site to subject.
- Confirm the subject has no AEs that would warrant discontinuation of the IP.
- Site should discuss any new or ongoing conmed(s) and determine if the use of any warrant having the subject stop IP application or not.
- For any female subject of childbearing potential that site should discuss and confirm the subject has continued her methods of ensuring pregnancy does not occur. Any deviation from these methods should be discussed further and the site should determine if IP should be halted or contact the medical monitor or Arcutis if they have any questions. A pregnancy test can be performed at the next onsite visit (this is applicable to prior visits being missed due to COVID-19 as well).
- Subjects are approved to continue dosing for up to 14 days past Week 4 until they return the clinic for the Week 4 visit. After this, sites should reach out to the Medical Monitor and/or Arcutis directly for approval to have subjects continue dosing.
- All the above discussions must be documented in the source.

d. If available, home health nurse visits could be considered for collection of Vital Signs and Clinical Labs.

e. In the event a subject is quarantined, has symptoms, or is confirmed positive for COVID-19, it is the Sponsor's opinion that IP can continue, assuming no other contraindications.

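### Appendix 6 item 5c pre-approves up to 14 days of dosing past a delayed Week 4 visit, with no weight, CDI-2, laboratory value or individual Medical Monitor review as a condition

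*Protocol*

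**What the plan says.** Item 5 of the remote-data guidelines in Protocol Appendix 6 covers a child who cannot return within the Week 4 window. Items 5a and 5b ask for the current consent form with its addendum, and for contact about continued dosing and diaries. Item 5c then states: "Subjects are approved to continue applying IP post Week 4 as long as the following have been discussed with the subject". The topics are drug supply, absence of an adverse event that would justify stopping, concomitant medication, and contraception where relevant, all documented in source. The approval runs for up to 14 days past Week 4. Only then comes the request for individual approval: "After this, sites should reach out to the Medical Monitor" and/or the sponsor.

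Other text bears on the same situation:

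- Item 2: "Study visits and procedures must be followed per protocol whenever possible". The Remote Data Collection section lists the CDI-2 as collectable remotely and weight as not collectable remotely.
- Item 2 also says "Any specific changes in study conduct that deviate from the protocol should be communicated to the IRB and Sponsor", and adds "It is prudent to receive IRB guidance or approval if a deviation is known to occur in advance (i.e., extending IP application" among its examples.
- Item 3 asks for Medical Monitor guidance "If a delayed clinic visit cannot be completed within 14 days of the protocol specified visit window".
- Item 5d: where available, "home health nurse visits could be considered for collection of Vital Signs and Clinical Labs".
- Section 9.6 requires prior sponsor and IRB/EC approval of deviations, except in emergencies, and reporting of those that occur.
- Section 7.9 keeps its stopping rules and its immediate Medical Monitor contact for events of concern.

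**The concern.** Sections 6.6 and 7.9 act on measured values: weight loss above 5% and a CDI-2 total of 34 (both discretionary), and a confirmed, drug-related Grade 3 laboratory abnormality (mandatory stop). Week 4 is when weight and CDI-2 are next due, and it is the only scheduled laboratory draw after dosing starts. Item 5c lets dosing run past that check without making any of these values a condition. The rules remain in force, but the values that would trigger them may not exist.

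Section 4.3.5 names weight loss and psychiatric events as risks of oral roflumilast. Section 4.4 counts weight, laboratory tests and the mood questionnaire among the practices that protect subjects. A conversation about adverse events may not reveal an unmeasured weight loss or laboratory change in a child of 6 to 11. What is at stake is individual safety oversight during the extra days. No effect on the PK, safety or efficacy analyses is claimed.

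**Working it through.** **Inputs.** Planned dosing is 28 days (Synopsis). Week 2 is Day 14 ± 1, so Day 13 to 15. Week 4 is Day 28 ± 3, so Day 25 to 31. Screening is up to 21 days before Day 1, and its laboratory results stand in for Baseline when Baseline falls within 3 weeks (section 2, footnote b; section 7.1.5). The extension is up to 14 days (item 5c).

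**Step 1: dosing limit.** 28 + 14 = Day 42, which is 14/28 = 50% more dosing days than planned.

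**Step 2: what the protocol acts on, against what item 5c requires.**

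| Value | Where it is used | Condition in 5c? | Other route |
|---|---|---|---|
| Adverse events | 6.6, 7.9 | Yes | – |
| Weight loss >5% | 6.6, discretionary | No | 5d, if available and if vital signs include weight |
| CDI-2 total of 34 | 6.6 and 7.9, discretionary | No | Remote collection, already called for by item 2 |
| Grade 3 laboratory abnormality | 7.9, mandatory if confirmed and related | No | 5d, if available; unscheduled tests (7.1.5) |

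Section 7.1.3 lists weight under vital signs, but the Schedule names it separately. Whether 5d covers weight is therefore unclear.

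**Step 3: age of the last scheduled value.**

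| | Ordinary, nominal | Ordinary, longest in window | At Day 42 under 5c | Added by 5c |
|---|---|---|---|---|
| Weight | 28 − 14 = 14 days | 31 − 13 = 18 | 42 − 14 = 28 (27 to 29) | 28 − 14 = 14, or 29 − 18 = 11 |
| Laboratory tests, Screening sample at the 21-day limit | 21 + 27 = 48 | 21 + 30 = 51 | 21 + 41 = 62 | 62 − 48 = 14, or 62 − 51 = 11 |

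If Week 2 was also missed, the last scheduled weight at Day 42 dates from Day 1 and is 42 − 1 = 41 days old. The CDI-2 has the same ages as weight, but only if the remote route is not used. For laboratory tests, the ordinary schedule already accounts for 48/62 = 77% of the age at Day 42.

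**Step 4: timing of Medical Monitor involvement.** Item 5c seeks approval to continue after Day 42. Item 3's contact applies if the visit cannot be completed by 28 + 3 + 14 = Day 45, and may come earlier if that is foreseen. Neither requires an individual review at nominal Week 4.

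**Step 5: scale.** One child is 1/20 = 5% of the planned sample. The number delayed is not predictable from the documents.

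**The case against.** The case for leaving the text alone is substantial.

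- **A decision has been made.** Item 5c is sponsor text in an amendment that itself needs IRB approval. The first 14 days are approved prospectively and bounded, which is a reasonable choice when sites may close. A reader might infer that nobody approves these days until Day 42; the documents do not support that. Only the case-by-case approval waits.
- **Section 9.6 may demand more.** It requires prior sponsor and IRB/EC approval of deviations, and item 2 uses extended application as an example of a deviation. If 9.6 governs, a sponsor decision comes first. The more specific 5c may override it, since it tells sites that continuation is already approved. Either way, 9.6 requires no measurement and no Medical Monitor review.
- **Item 2 already calls for the CDI-2.** A reader might infer that a compliant site can dose with no current safety measurement at all. That requires reading 5c in isolation: skipping a feasible remote CDI-2 would breach item 2. What is missing is a requirement to score it before continuation.
- **Laboratory results gate none of the planned days.** The only scheduled draw after dosing starts falls at the end of dosing. This stands, and a reader should not attribute the full 62 days to 5c. The difference is that dosing ordinarily ends when that check falls due, whereas here it continues.
- **Longer exposure is already envisaged.** An extension study of up to 24 weeks exists, so the extra exposure is not unusual. Entry to it, however, follows the Week 4 visit, where weight, CDI-2 and laboratory tests are scheduled.
- **Harm is not shown.** The named risks come from oral tablets in mostly middle-aged and older COPD patients, and much of the topical evidence is redacted. This stands.

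**Conclusion.** The point holds in a limited form. Item 5c approves dosing to nominal Day 42 with an adverse-event check, but makes no current weight, CDI-2, laboratory value or individual Medical Monitor review a condition of passing the Week 4 safety check. Items 2 and 5d and sections 7.9 and 9.6 narrow the gap without closing it.

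The size is modest. At Day 42 the last scheduled weight and the oldest possible laboratory result are each 14 days older than on the nominal schedule, or 11 days older than the longest in-window gap.

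The documents do not support the inference that the extra 14 days are unsafe or that the stopping rules are waived: the added risk cannot be judged from them, and the rules still apply. The day counts assume that no unscheduled or home-nurse measurement was taken. The consent form addendum and the IP Handling Plan were not available and could address part of this. This is a cheap improvement of optional to moderate priority.

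**What to change.** Add two lines to the item 5c list:

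1. The scheduled CDI-2 is done remotely at nominal Week 4 and scored before continuation is confirmed.
2. If Week 4 weight or safety laboratory tests have not been obtained, the Medical Monitor is notified at nominal Week 4 rather than after 14 days. They can be obtained by the 5d route or at a drug pick-up, which 5c already foresees ("if not ask the subject to return to the site to pick up additional IP").

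State in 5d that vital signs include weight. Because section 7.1.3 asks for the same scale throughout, a weight from another scale should be flagged. No nurse visit becomes mandatory and no automatic stop is added. Whether dosing continues stays with the investigator, Medical Monitor and sponsor.

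The cost is appendix wording, scoring a 17-item questionnaire that is already scheduled and approved for remote use, and one message alongside the deviation report that item 2 already asks for. The downside is slightly more site and Medical Monitor work for any delayed child.

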9.5.	Children's Dermatology Life Quality Index (CDLQI)	16
10.	Safety Analysis	17
10.1.	Exposure and Compliance	17
10.2.	Adverse Events	17
10.3.	Local Tolerability Assessment	18
10.4.	Vital Signs	19
10.5.	Physical Examination	19
10.6.	Prior and Concomitant Medications	19
10.7.	Laboratory Tests	20
10.8.	Electrocardiogram	21
10.9.	Children's Depression Inventory 2 (CDI-2).....	21
10.10.	Dermal Imaging.....	21
11.	Pharmacokinetics	21
12.	Planned Tables, Figures, and Listings	22

List of Abbreviations

AE	Adverse Event
ATC Class	Anatomical/Therapeutic/Chemical Class
BSA	Body Surface Area
CDI 2	Children's Depression Inventory 2
CDLQI	Children's Dermatology Life Quality Index
COVID-19	Coronavirus Disease 2019
CSR	Clinical Study Report
ECG	Electrocardiogram
EDC	Electronic Data Capture
EOS	End of Study
FOCBP	Female of Childbearing Potential
IGA	Investigator Global Assessment
I-IGA	Intertriginous Investigator Global Assessment
ITT	Intent to Treat
LSR	Local Skin Reactions
µg	Microgram
MedDRA	Medical Dictionary for Regulatory Activities
PDE-4	Phosphodiesterase 4
PASI	Psoriasis Area and Severity Index
PK	Pharmacokinetics
QD	Once Daily (“quaque die”)
SAE	Serious Adverse Event
SAP	Statistical Analysis Plan

TEAE	Treatment Emergent Adverse Event
WHO	World Health Organization
WI-NRS	Worst Itch Numeric Rating Score

1. Introduction

Arcutis, Inc. is conducting a study under the protocol name “An Open-Label, 4-Week, Phase 2, Maximal Usage Pharmacokinetics and Safety Study of ARQ-151 Cream 0.3% Administered QD in Pediatric Subjects (aged 6 to 11 years old) with Plaque Psoriasis”. The study background, design and subject assessments for the study are described in the study specific protocol.

The statistical methods to be implemented during the analyses of data collected within the scope of this study (ARQ-151-215) will be outlined in this document. The purpose of this plan is to provide specific guidelines from which the statistical analysis will proceed. Any deviations from this plan will be documented in the clinical study report.

This version of the Statistical Analysis Plan (SAP) addresses this study as described in Amendment 1 Final dated 22 January 2021 of the study protocol.

2. Study Rationale and Objectives

2.1. Study Rationale

The past 15 years have witnessed a transformation in the systemic treatment of moderate to severe psoriasis with the advent of biological therapies. However, for patients with milder forms of disease, best treated with topical options, the therapeutic landscape has not significantly changed in several decades. Topical steroids come in all shapes and forms, but the lower potency steroids are not effective and the higher potency steroids are best with issues of local skin atrophy and the potential for hypothalamic-pituitary axis suppression when applied over larger body surface areas and for prolonged periods of time. Vitamin D has been the other staple of topical psoriasis treatment, but it is irritating, not suitable for use on the face or intertriginous areas, and its efficacy is rather modest. Hence, there is a substantial medical need for additional topical approaches in the treatment of psoriasis. The study Sponsor is developing a topical cream formulation of roflumilast for the treatment of chronic plaque psoriasis. Phase 2 results suggest that ARQ-151 may be a highly efficacious and well-tolerated topical treatment for psoriasis. Accordingly, a phase 3 program is ongoing evaluating ARQ-151 cream 0.3% for the treatment of plaque psoriasis in subjects 2 years of age and older. The present study is a maximal use pharmacokinetic trial with the to-be-marked formulation. The study is designed to ensure that the expected target patient population for ARQ-151 is properly represented, as well as to ensure that a suitable number of subjects with plaque psoriasis are evaluated and that PK is adequately characterized.

2.2. Study Objectives

2.2.1. Primary Objectives

The primary objectives are:

- To evaluate the systemic exposure and characterize the plasma pharmacokinetic (PK) profile of ARQ-151 cream 0.3% and its major N-oxide metabolite, in pediatric subjects with plaque psoriasis involving body surface areas (BSA) of at least 3%.
- To evaluate the safety of ARQ-151 cream 0.3% applied QD to pediatric subjects with plaque psoriasis involving BSA of at least 2%.
- To explore the efficacy of ARQ-151 cream 0.3% applied QD for 4 weeks to pediatric subjects with plaque psoriasis involving BSA of at least 2%.

3. Study Design

This is a phase 2, open label maximal usage PK and safety study of ARQ-151 cream 0.3% in pediatric subjects (ages 6 to 11 years old) with plaque psoriasis.

At entry, subjects will have at least 2% BSA involvement (excluding the scalp, palms, soles), except for a subset of evaluable subjects who consent to a PK sampling for maximal usage evaluation that will have at least 3% BSA involvement (excluding the scalp, palms, soles), and both groups of subjects will have a minimum IGA of Mild ('2').

Subjects who discontinue the study may be replaced.

Subjects/caregivers will apply ARQ-151 cream 0.3% QD for 28 days to all affected areas of plaque psoriasis and any newly appearing plaque psoriasis lesions that arise during the study, except on the scalp. Subjects/caregivers should maintain treatment of these areas with study drug for the duration of the study regardless of whether treatable areas of plaque psoriasis clear prior to Week 4. The palms and soles will be treated but will not be counted towards any measurements of efficacy (PASI, IGA, I-IGA, BSA).

3.1. Schedule of Visits and Assessments

Study Procedure	Screening	Baseline Day 1	Wk 2 Day 14	Wk 4 Day 28/ET	Wk 5 Day 35
Visit	1	2	3	4	5
Visit Window	-3 weeks		+/- 1 day	+/- 3 days	+/- 3 days
Informed consent/assent	X				
Demographics	X				
Medical and surgical history	X				
Physical examination ^a	X	X		X	
I/E criteria	X	X			
Hematology, Serum Chemistries, and Urine Analysis ^b	X	X		X	
Vital signs, weight, height ^c	X	X	X	X	
IGA, I-IGA, PASI, BSA, WI-NRS, CDLQI ^d	X	X	X	X	
Local cutaneous tolerability assessment (including Berger & Bowman and subject-rated stinging/burning) ^e		X	X	X	
CDI-2	X	X	X	X	
Serum pregnancy test ^f	X				
Urine pregnancy test ^f		X		X	
Resting 12-lead ECG	X			X	
PK sampling ^g			X	X	
Drug application and subject/family training in clinic ^h		X	X		
Dispense investigational product kit ⁱ		X	X		
Weigh investigational product tubes ^j		X	X	X	
Dispense/review diary		X	X	X	
Adverse event assessment ^k	X	X	X	X	
Concomitant medications	X	X	X	X	
Optional photography ^l		X	X	X	
Study Exit ^m					X

^a Limited physical examination: skin, lungs, and heart only.

^b To be collected at Screening, Baseline, and Week 4. If Baseline is within 3 weeks of Screening, the Screening results will be utilized.

^c Height will be measured at every visit (see Protocol Section 7.1.3 for the recommended procedure). Weight will be collected on every visit. Weight should be obtained using a calibrated weight scale

and the same scale should be used for a subject throughout the duration of the study. The subject should remove shoes and heavy clothing (sweaters or jackets), and empty pockets. The subject should stand with both feet in the center of the scale with their arms at their side and hold still. Record the weight to the nearest decimal fraction (for example, 55.5 pounds or 25.1 kilograms). Measure the weight in triplicate and report the average weight in EDC.

- ^d BSA, IGA affected by plaque psoriasis will be determined to qualify for study entry (Screening and Baseline) and will be measured at the Week 2 and Week 4 visits. Scalp, palms and soles should be excluded from consideration in these assessments. Additionally, Intertriginous Area-IGA (I-IGA), PASI, and WI-NRS will be evaluated. WI-NRS pruritus assessment will be completed by subjects \geq 8 years old, or by parent/caregiver for subjects < 8 years old. All other assessments will be performed by the Investigator or study staff, as appropriate.
- ^e Local tolerability assessments should be recorded prior to study drug application for the Investigator assessment of skin irritation (Berger and Bowman skin irritation score) and 10-15 minutes post-drug application for the subject's '0-3' burning/stinging assessment (subject-rating completed by the subject or parent/caregiver). At the Week 4 visit, only the Investigator assessment of skin irritation will be performed. Note for investigator tolerability assessments: reactions at the site of product IP application, which may occur post-Baseline, should be differentiated from the preexisting inflammation associated with the subject's psoriasis.
- ^f For females that have started menstruation, a serum pregnancy test will be performed during Screening. A urine pregnancy test will be administered to all females of child-bearing potential. A negative result is required for continued participation in the study, and results must be available prior to dispensing of study drug.
- ^g All enrolled subjects will have a trough PK sample collected at the Week 4 visit. A subset of 6 subjects who consent will provide an additional PK sample pre-dose (within 1 hour) at the Week 2 visit.
- ^h Subjects/caregiver to apply assigned IP in clinic at Baseline and Week 2. All Investigator assessments should be completed prior to IP application.
- ⁱ The number of kits to be dispensed is based on %BSA affected. See IP Handling Manual for details. Site should review IP kit to ensure sufficient IP is available until the next visit and only dispense additional IP if needed.
- ^j Every tube should be weighed and recorded when dispensed and returned.
- ^k Any emergent AEs will be followed in the clinic for up to 1 month at the Investigator's discretion until resolved or otherwise judged as clinically stable.
- ^l Photography is planned to be performed at selected investigational sites. Photography will be optional. All efforts will be made to de-identify the subjects.
- ^m Subjects who enroll into the open label extension study (ARQ-151-306) will complete the study at Week 4; subjects that do not enroll into ARQ-151-306 will complete the study with a Week 5 Telephone Follow-up. The Week 5 Telephone Follow-up is a call to the subjects to follow-up on any continuing adverse events related to the study drug. Telephone call also assesses any emergent adverse event post-Visit 4. Any emergent AEs will be followed in the clinic for up to 1 month at the Investigator's discretion until resolved or otherwise judged as clinically stable.

4. Determination of Sample Size

Approximately 20 male and female subjects ages 6 to 11 years old with plaque psoriasis:

- All subjects must have at least 2% BSA psoriasis involvement at Baseline
- However, a subset of 6 evaluable subjects who consent to a PK sample for maximal usage evaluation will have at least 3% BSA involvement at Baseline (excluding the scalp, palms, soles)
 - PK evaluable subjects (in the maximal usage subset) are defined as those that have PK results at Week 2. Unevaluable subjects may be replaced.
- All subjects must have at least Mild ('2') psoriasis severity based on IGA at Baseline

This sample size is considered adequate for PK and safety evaluation. The sample size was not powered based on data for the efficacy endpoints to provide statistical significance.

5. Statistical Methods

Summaries may be generated for regulatory interaction prior to the completion of the study and an interim report may be written at that time. The statistical analyses will be reported using summary tables, figures and listings (TFLs). Numbering for TFLs will be based on the recommended numbering convention provided by the International Conference on Harmonisation.

Continuous variables will be summarized with means, standard deviations, medians, minimums and maximums. Categorical variables will be summarized by counts and percent of subjects in corresponding categories. Unless specified otherwise, baseline results will be defined as the closest measurement taken prior to first dose of study medication. When applicable, unscheduled visits will be used in the determination of baseline values. Missing values are not considered for percent calculations, unless stated otherwise. In those cases, footnotes will specify the percent calculation. No formal inferential statistics will be performed for this open-label study.

Individual subject data obtained via the electronic data capture (EDC) system and from external vendors will be presented in by subject listings.

The analyses described in this plan are considered *a priori*, in that they have been defined prior to database lock. Any analysis added after the database lock will be considered *post hoc* and exploratory. *Post hoc* analyses will be labeled as such on the output and identified in the CSR. All analyses and tabulations for the CSR will be performed using

SAS® version 9.4 or higher. Tables will be presented in .rtf and .pdf format. Listings will be presented in .pdf format. Upon completion, all SAS programs will be validated by an independent programmer. The validation process will be used to confirm that statistically valid methods have been implemented and that all data manipulations and calculations are accurate. Checks will be made to ensure accuracy, consistency with this plan, consistency with tables and consistency between tables and corresponding data listings.

6. Analysis Populations

Subjects who enroll into the study need to sign informed consent and receive at least one confirmed dose of investigational product.

The Safety population will include all subjects who are enrolled and received at least one confirmed dose of investigational product. This population will be used for safety and efficacy analyses.

The Pharmacokinetic (PK) population will include all subjects who have received at least 1 confirmed dose of IP with sufficient plasma concentrations of roflumilast to define a profile, as determined by the pharmacokinetics.

7. Study Population

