## 6.7 Replacement of Subjects that Withdraw or are Discontinued from the Study

Subjects that withdraw or are discontinued from the study prior to the Week 4 Visit, may be replaced.

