### 8.1 Statistical Methods

The methodology presented below is a summary of the more detailed analysis plan that will be presented in the Statistical Analysis Plan (SAP). The SAP will be finalized before the database is locked. Any changes to the methods described in the final SAP will be described and justified in the clinical study report.

All statistical processing will be performed using SAS® (Version 9.4) unless otherwise stated. No interim efficacy analyses are planned.

Descriptive statistics will be used to provide an overview of the safety, efficacy, and pharmacokinetic results. For categorical parameters, the number and percentage of subjects in each category will be presented. The denominator for percentage will be based on the number of subjects appropriate for the purpose of analysis. For continuous parameters, descriptive statistics will include n (number of subjects), mean, standard deviation (SD), median, minimum, and maximum. No formal inferential statistics will be performed for this open-label study.

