### **8.1.3 Determination of Sample Size**

The sample size will be approximately 20 subjects.

This sample size is considered adequate for safety and PK evaluation. The sample size was not powered based on data for the efficacy endpoints to provide statistical significance.

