8.3. Handling of Dropouts or Missing Data

Subjects that withdraw or are discontinued from the study prior to Week 4 Visit, may be replaced. Unless described otherwise in subsequent sections, analyses will be carried out with the data available using no imputation for missing data. A description of how missing data will be handled for select endpoints is included below.

8.3.1. Coronavirus 19

Due to coronavirus disease 19 (COVID-19) outbreak during the course of the study, there may be several subjects who will have missing assessments which could affect the analysis. Subjects who are unable to attend a study visit due to COVID-19 will be documented in the protocol deviation log. The protocol deviation date will be used as the COVID-19 affected date (or visit). If a subject reports an adverse event of COVID-19,

then the event start date will be used as the affected date. In the event that a subject has an affected COVID-19 date from both sources, the earlier of the dates will be used.

Subjects who were affected by COVID-19 will be summarized in a data listing. The listing will contain the following information: subject number, treatment, gender, age, total study duration, exposure to study treatment, any COVID-19 related adverse events, completion/discontinuation of the study, and reasons for discontinuation.

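### PASI50, PASI75, IGA success and WI-NRS success are observed-case percentages under a Safety-population label; one missing-as-non-response line per table would bound the effect of missing assessments

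*SAP*

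**What the plan says.** - **Denominator.** SAP Section 5 states: "Missing values are not considered for percent calculations, unless stated otherwise". It asks for an explanatory footnote only where a table departs from that default. Protocol 8.1 is less specific: "The denominator for percentage will be based on the number of subjects appropriate for the purpose of analysis".
- **Missing data.** Under SAP 8.3, "analyses will be carried out with the data available using no imputation for missing data", unless a later section says otherwise. The section announces missing-data rules for selected endpoints, but what follows is a COVID-19 subsection that produces a listing. No efficacy endpoint receives a rule.
- **Responder endpoints.** SAP 9.1 (PASI50, PASI75), 9.2 (IGA success) and 9.4 (WI-NRS success, among children with a baseline score of at least 4) ask for counts, proportions or rates by visit. None names a different denominator.
- **Population.** SAP Sections 6 and 8 use the Safety population for efficacy. One confirmed dose is enough to belong to it.
- **Replacement.** Protocol 6.7: "Subjects that withdraw or are discontinued from the study prior to the Week 4 Visit, may be replaced". SAP 8.3 repeats this.
- **Sources of a value for a child who leaves or misses a visit.** Protocol 7.5 asks for the Week 4 procedures at an early termination visit, and the schedules in both documents place early termination in the Week 4 column. SAP 8.4 uses unscheduled assessments when scheduled ones were not collected.
- **Status of efficacy.** It is exploratory (SAP 8.1). "The sample size was not powered based on data for the efficacy endpoints to provide statistical significance", and "No formal inferential statistics will be performed for this open-label study".

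**The concern.** The table label and the denominator do not match. A reader who sees a PASI75 percentage headed Safety population will take it as a percentage of treated children. Under the default rule it is a percentage of treated children who have a PASI at that visit. With about 20 children and no control arm, two or three missing assessments move the percentage visibly, and no comparison group with similar missingness offsets them.

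Some of the reasons for removal in Protocol 6.6, such as adverse events, need for prohibited medication or repeated non-compliance, could plausibly go with poorer response. Appendix 6 of the protocol bars remote IGA and PASI, so a missed clinic visit normally means that neither is available. WI-NRS can be collected remotely and is less exposed.

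The stakes are modest but not nil. Exploring efficacy appears under the primary objectives in both documents (Protocol 5.1.1, SAP 2.2.1), and SAP Sections 5 and 8.5 allow summaries to be produced for regulatory interaction.

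**Working it through.** **Inputs from the documents.** One arm; "The sample size will be approximately 20 subjects" (Protocol 8.1.3). The documents give no power, precision, response rate or dropout rate, so the plan has no figure of its own to reproduce.

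**Assumed inputs.** d = 1 to 4 treated children without an assessment at the visit, and an observed response of about 30% to 70%.

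**Formulas.** Let r be the responders among assessed children, n the number assessed and N the number treated. Let f = (N − n)/N be the share missing.
- Observed-case percentage (the plan): p_obs = r/n.
- Missing counted as non-response: r/N.
- True percentage in all treated children: (1 − f) × p_obs + f × p_miss, where p_miss is the unknown response among missing children.
- Overstatement by the observed-case figure: p_obs minus the line above = f × (p_obs − p_miss).

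**Step 1: largest gap without replacement, N = 20.**

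| Missing | Observed case | Missing as non-response | Gap (points) |
|---|---|---|---|
| 1 | 10/19 = 52.6% | 10/20 = 50.0% | 2.6 |
| 2 | 9/18 = 50.0% | 9/20 = 45.0% | 5.0 |
| 3 | 8/17 = 47.1% | 8/20 = 40.0% | 7.1 |
| 4 | 8/16 = 50.0% | 8/20 = 40.0% | 10.0 |

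**Step 2: dependence on the unknown response of missing children, p_obs = 50%.**

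| p_miss | f = 10% (2 of 20) | f = 20% (4 of 20) |
|---|---|---|
| 0% | +5.0 | +10.0 |
| 25% | +2.5 | +5.0 |
| 50% | 0 | 0 |
| 75% | −2.5 | −5.0 |

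For example, 0.10 × (50 − 25) = 2.5 points. The sign depends on whether missing children respond less or more often than assessed ones.

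**Step 3: the role of replacement.** Suppose each child lost is replaced, so that 20 are assessed and N = 20 + d. With 10/20 = 50.0% observed, the figure over all treated children is 10/21 = 47.6%, 10/22 = 45.5%, 10/23 = 43.5% and 10/24 = 41.7% for d = 1 to 4. At d = 4 the gap is 50.0 − 41.7 = 8.3 points, against 10.0 without replacement (Step 1). Replacement therefore does not create or enlarge the gap. It restores the number assessed to 20, so the table no longer looks short.

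**Step 4: range and scale.** Over the assumed ranges, the largest possible overstatement runs from 1.4 points (6/20 = 30.0% against 6/21 = 28.6%) to about 14 points (11/16 = 68.75% against 11/20 = 55.0%). The exact 95% interval for 10/20 is 27% to 73%, so sampling uncertainty is much larger.

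**The case against.** A reader might infer something stronger: that the percentages describe completers only, that they are inflated in favour of the drug, and that replacement drives this. The documents do not support any of the three.

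- **Completers only.** A child who leaves early should have PASI, IGA and WI-NRS at the early termination visit, and SAP 8.4 lets unscheduled values stand in. This part of the objection stands. What remains is narrower: a child lost without a termination visit has no value, an unscheduled value helps only if one was taken, and the SAP never says in words that early termination values are analysed as Week 4.
- **Direction.** Nothing in either document shows that missing children respond less often. The one cause of missing assessments that SAP 8.3 expressly anticipates is COVID-19, which may be unrelated to response; counting those children as failures could bias the rate downward. This stands too, and it is why the added line belongs beside the observed-case figure and not in its place.
- **Replacement.** Replaced children stay in the Safety population by definition, and Step 3 shows a smaller gap with replacement than without. This stands.

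It can also be said that observed-case description is a legitimate pre-specified choice in an exploratory study, and that counts, disposition with reasons and subject listings let a reader rebuild the figures. That is fair, but only in part. Disposition counts children who discontinued, not values missing by endpoint and visit, and the SAP requires a footnote on the percentage only when the default is not used.

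**Conclusion.** The responder percentages are observed-case figures presented under an all-treated label. They are conditional on having an assessment. They may overstate response if missing children respond less often than assessed ones. At 50% observed response with 2 to 4 of 20 missing, the overstatement is at most 5 to 10 points, reached only if none of the missing children responded. With complete data, or equal response in missing children, there is none. These sizes rest on assumed missingness and response rates because the documents give neither.

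The documents do not support the claim that the figures tend to be inflated or that replacement inflates them. Importance is low: the primary endpoints are PK, safety and tolerability, efficacy is exploratory and descriptive, and no decision rule uses these percentages. The change is a cheap improvement, not the correction of an error.

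**What to change.** Before database lock, by SAP amendment or addendum:

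1. In each responder table (PASI50, PASI75, IGA success, WI-NRS success), keep the observed-case percentage and show n assessed and N treated beside it.
2. Add one line with N = all Safety-population children, including those who were replaced, and count a missing assessment as non-response. For WI-NRS success, N is those with a baseline score of at least 4. The line is a lower bound on response in all treated children, so together with the observed-case figure it shows how far missing assessments could lower the result.
3. State in one sentence the visit to which early termination values map and that they are analysed there.

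The cost is one line per table and a slightly less favourable second figure, which may be too conservative where values are missing for COVID-19 reasons; a footnote with the number of such children would make that clear. Timing matters because SAP Section 5 classes any analysis added after lock as post hoc.
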